7.2 PARTICIPANT DISCONTINUATION/WITHDRAWAL FROM THE STUDY

Study Treatment Discontinuation

Under certain circumstances, an individual participant’s receipt of study product will be prematurely or permanently discontinued. Specific events that will result in stopping a participant’s infusions or VOR dosing in this study include:

- Failure to meet requirements established for safety assessment
- Withdrawal from the study
- Pregnancy
- Grade 3 AE assessed as related to the study products (with the exception that self-limited Grade 3 solicited reactogenicity does not require discontinuation from VRC07-523LS administration).
- Grade 4 AE assessed as related to the study products
- Intercurrent illness that is not expected to resolve prior to the next scheduled VRC07-523LS administration which is assessed by the study PI (or designee) to require withdrawal from the administration of VRC07-523LS
- Repeated failure to comply with protocol requirements
- Co-enrollment into a study in which other investigational research agents will be administered before the participants has completed the follow-up visits after receiving the last study product
- Investigator discretion
- Clinically significant hypersensitivity or infusion-related reaction including but not limited to type 1 hypersensitivity reaction, urticaria, or serum sickness associated with study treatment.

If the study Principal Investigator (or designee) decides that a participant should be withdrawn from study treatment, the protocol team must be alerted within 24 hours. All participants who discontinue treatments should comply with protocol-specified visits and follow-up as required by the protocol and evaluation by the study PI (or designee). The only exception to this requirement is when a participant withdraws consent for all study procedures or loses the ability to consent freely (i.e., is imprisoned or involuntarily incarcerated for the treatment of either a psychiatric or physical illness).

If a participant is withdrawn before completing the study, the reason for withdrawal must be documented appropriately in the study documents.

Early Study Discontinuation

A participant may withdraw or be withdrawn from the study if any of the following occurs:

- Failure by the participant to attend multiple clinic visits.
- Failure to receive the first VRC07-523LS infusion.
- Development of an illness that requires treatment with medications prohibited in this study.

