8.3.5 ADVERSE EVENT REPORTING

Adverse events will be graded according to the DAIDS Table for Grading the Severity of Adult and Pediatric Adverse Events (DAIDS AE Grading Table), corrected Version 2.1, July 2017, on the DAIDS RSC website at <http://rsc.tech-res.com/clinical-research-sites/safety-reporting/daids-grading-tables>

Participants will be monitored for adverse events. Toxicities will be characterized in terms including duration, intensity, and time to onset. Safety endpoints will include all adverse experiences, in addition to laboratory safety assessments, and vital signs. All AEs will be recorded on the appropriate study form. All AEs will be recorded in the database if any of the following criteria have been met:

- Study-related grade ≥ 1 AEs
- Grade ≥ 3 AEs
- Autoimmune-related AEs regardless of grade
- HIV viral loads ≥ 50 copies/mL
- Infusion reactions regardless of grade
- AEs that led to a change in study intervention regardless of grade
- AEs meeting SAE definition or EAE (Expedited Adverse Event) reporting requirement

Grade 1 or 2 Toxicity

Participants who develop a Grade 1 or 2 AE or lab toxicity that occurs following a VRC07 infusion or dose of VOR dosing that is thought to be possibly, probably, or definitely related to study treatment should be discussed with the study team. Grade 1 or 2 AEs that may be related to the VRC07-523LS or VOR should be handled according to standard clinical practice and documented. Participants who experience a Grade 1 or 2 AE that is judged related to the study treatments by the study PI (or designee), may continue study treatment at the discretion of the study PI (or designee).

Participants who experience a Grade 1 or 2 AE that is judged not to be related to the study drug/product by the study PI (or designee), may continue study treatment at the discretion of the study PI (or designee).

Grade 3 Toxicity

For participants who develop a Grade 3 AE following administration of VRC07-523LS or VOR that is judged by the study PI (or designee) to be at least possibly study treatment-related, the protocol team, inclusive of the DAIDS Medical Officer, must be notified within 24 hours. Participants experiencing Grade 3 AEs should be followed closely and if the AE does not return to Grade ≤ 2 within 2 weeks, the study team should again be notified within 24 hours and the SMC will be notified. Continued receipt of study

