products is at the discretion of the study PI (or designee) in consultation with the protocol team and the SMC.

For participants who experience a Grade 3 AE that is judged not related to the study treatment by the investigator, continued study participation is at the discretion of the study PI (or designee) in consultation with the protocol team and SMC.

Grade 4 Toxicity

For participants who develop a Grade 4 AE following administration of VRC06-523LS or VOR that is judged by the study PI (or designee) to be at least possibly study treatment-related, the protocol team, the DAIDS Medical Officer and SMC must be notified within 24 hours. Participants experiencing Grade 4 AEs should be followed closely with additional clinical assessments and laboratory testing as clinically indicated. If the AE does not return to Grade ≤ 2 within 2 weeks, the protocol team and SMC should again be notified within 24 hours.

All study treatments will be discontinued in the event of Grade 4 AEs possibly related to study treatment.

Local or Systemic Reactions to VRC07-523LS

Grade 1 or 2

Local reactions of mild (Grade 1) or moderate (Grade 2) severity will usually resolve spontaneously. If needed, they may be managed with local application of cold packs, oral acetaminophen, oral non-steroidal anti-inflammatory agents, or a combination of these measures as appropriate.

NOTE: Topical steroids should not be applied to the infusion site.

Grade 3 or 4

For severe (Grade 3) or potentially life-threatening (Grade 4) local reactions, the protocol team, inclusive of the DAIDS Medical Officer, must be notified within 24 hours. For Grade 4 local reactions, definitive medical and/or surgical intervention should be undertaken as appropriate. Further infusions will not be administered.

Systemic Reactions

The protocol team, inclusive of the DAIDS Medical Officer, must be contacted within 24 hours for any non-local Grade 3 or 4 systemic reactions thought definitely, possibly, or probably related to the VRC07-523LS infusion or the administration of VOR doses. Further infusions and VOR doses will not be administered.

If an adverse event of special interest (AESI) occurs (see section 8.3.8), the study coordinator, in collaboration with the study PI (or designee), will evaluate the severity and seriousness of the AE and the relationship to the study treatment, and will document the findings.

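### Section 7.2 stops dosing after a related Grade 3 adverse event, but the Grade 3 paragraph of section 8.3.5 lets it continue at the investigator's discretion

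*Combined protocol and SAP*

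**What the plan says.** Section 7.2, under Study Treatment Discontinuation, opens its list with "Specific events that will result in stopping" a participant's "infusions or VOR dosing in this study include". One entry is a "Grade 3 AE assessed as related to the study products (with the exception that self-limited Grade 3 solicited reactogenicity does not require discontinuation". The exemption names one product only: such reactogenicity "does not require discontinuation from VRC07-523LS administration". It is silent on VOR.

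Section 8.3.5 has its own Grade 3 paragraph. It begins "For participants who develop a Grade 3 AE following administration of VRC07-523LS or VOR that is judged by the study PI" and applies where the event is thought at least possibly due to treatment. The protocol team, including the DAIDS Medical Officer, must be told within 24 hours. Notice to the SMC is expressly required if the event has not fallen to Grade 2 or lower within two weeks. Continued receipt of study "products is at the discretion of the study PI (or designee) in consultation with the protocol team and the SMC".

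The Grade 4 paragraph that follows is different: "All study treatments will be discontinued in the event of Grade 4 AEs possibly related to study treatment". Later in 8.3.5, a related Grade 3 or 4 systemic reaction ends both infusions and VOR. The paragraph on Grade 3 or 4 local reactions ends with "Further infusions will not be administered". Neither reaction paragraph repeats the exemption in 7.2.

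**The concern.** For one and the same event, one section ends dosing and another allows it. A related Grade 3 event is itself a primary safety event (sections 1.1 and 3), and section 2.3.2 says that participants gain no direct medical benefit. The rule for the individual participant should therefore be unambiguous.

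The study-wide pause in section 10.1.6 does not settle the matter. It needs two participants with a related event of Grade 3 or higher, or one related serious adverse event. A first, non-serious event does not trigger it, so it falls under the individual rules together with the SMC contact described in 10.1.6. VOR is taken at home every 72 hours, and the Grade 3 paragraph does not say that doses are withheld while the consultation runs.

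**Working it through.** **Do the two rules cover the same events?** Yes. Section 8.3.3.2 classes possible, probable and definite as related. Related in 7.2 and at least possibly related in 8.3.5 are therefore the same set. The parts of the letters of amendment that could be read change neither rule.

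**What happens to each kind of related Grade 3 event?**

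| Event | 7.2 | 8.3.5 Grade 3 paragraph | Other rule |
|---|---|---|---|
| Asymptomatic, non-haematologic laboratory finding | Stop | PI discretion, with consultation | Laboratory check before the Day 60 infusion (8.2); none within a series |
| Haematologic toxicity | Stop | PI discretion, with consultation | DLT rule stops both products from Grade 2 if confirmed and not clearly due to another reversible cause (8.3.5) |
| Symptomatic, non-haematologic event | Stop | PI discretion, with consultation | Meets the DLT definition if confirmed (8.3.5). That bullet states no dosing consequence, though 8.1 speaks of treatment discontinued for a DLT |
| Self-limited solicited systemic symptom | VRC07-523LS may continue; VOR not addressed | PI discretion, with consultation | Systemic-reaction rule ends both products (8.3.5) |
| Local reaction | Stop, unless self-limited and solicited | PI discretion, with consultation | The stop on infusions follows a sentence about Grade 4 only, so its reach to Grade 3 is unclear (8.3.5) |

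The first row is the main gap. Section 8.3.4 has Grade 3 laboratory findings reported as adverse events, and section 1.1 counts related ones in the primary endpoint. Safety chemistry is drawn at Days 7, 14, 29, 67, 74 and 89 (section 1.3). Section 2.3.1 lists raised creatinine and hyperglycaemia among VOR-related events seen in at least 10% of participants in the manufacturer's studies, without giving grades.

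The fourth row is the separate exemption conflict. Section 8.1 lists chills, headache and nausea as solicited systemic symptoms, so one self-limited episode receives three different answers.

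**How many VOR doses are at issue within a series?** Inputs: first dose two days after the infusion, then one every 72 hours, ten doses of 400 mg per series (sections 1.1 and 6.1.2). Dose days are 2 + 3k and 62 + 3k, for k = 0 to 9.

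- Day 7 or 67: 2 taken, 10 − 2 = 8 left; 8 × 400 = 3,200 mg.
- Day 14 or 74, counting that day's dose as taken: 5 taken, 10 − 5 = 5 left; 5 × 400 = 2,000 mg.
- Day 29 or 89: 10 taken, none left.

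**Could the site simply withhold supply?** In part. Under Letter of Amendment 2, two doses are dispensed on Day 0, and both have been taken by Day 7 (Days 2 and 5). The site can therefore withhold at Days 7 and 14. Five doses are dispensed on Day 60. Two have been taken by Day 67 (Days 62 and 65), so 5 − 2 = 3 are at home, for Days 68, 71 and 74.

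**Does a stated figure move?** No. The nearest is the upper limit of 0.22 in section 9.2, which reproduces as 1 − 0.05^(1/12) = 0.221 and does not depend on the dosing rule.

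**The case against.** The best reply is that both rules can be obeyed at once: the PI can use the discretion in 8.3.5 by stopping, and the Statement of Compliance bars unapproved departures from the protocol. This does not remove the conflict. The Grade 3 paragraph expressly contemplates continued dosing that 7.2 rules out. Investigator discretion also appears in 7.2, but there as a further reason to stop.

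Oversight is a fair point and stands in part. Section 10.1.6 has the SMC contacted directly about anything that affects participant safety, with interventions suspended or terminated depending on its response. Consultation with the SMC is part of the Grade 3 paragraph, and there is only one site. A reader might infer that a first event is left to the PI alone; these provisions do not support that. What they lack is a hold on dosing until the SMC has replied.

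On the exemption, 7.2 only says that stopping is not required, so the stricter systemic rule breaches nothing and is the more protective. That is correct. It still leaves the exemption without effect for systemic symptoms, although the pause rule in 10.1.6 carries the same exemption, which suggests that it was meant to operate.

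Three stronger readings are tempting:

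- **18 further VOR doses (18 × 400 = 7,200 mg) and a second infusion after a Day 7 event.** This needs no DLT or reaction stop, a passed or waived Day 60 laboratory check, and consultation that favours dosing. It is a stacked worst case.
- **A definite conflict for local reactions.** The stop may apply to Grade 4 only.
- **A contradiction over replacement.** Section 7.2 replaces anyone who does not complete all doses. Sections 7.1 and 9.2 provide for replacement only for non-toxicity reasons or reasons other than a Grade 3 or higher event. They never say that participants stopped for toxicity will not be replaced, so this is a separate and partly implied matter.

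**Conclusion.** The point holds and should be fixed. Sections 7.2 and 8.3.5 give incompatible dosing rules for related Grade 3 events, with no precedence stated and no hold pending consultation. In practice the gap is narrow: mainly asymptomatic, non-haematologic, related Grade 3 laboratory findings, with at most 8 VOR doses (3,200 mg) left in the current series. The exemption conflict is clear for solicited systemic symptoms and uncertain for local reactions.

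This assumes that no unread part of a letter of amendment alters either rule. No event probability is claimed: section 2.3.1 reports no Grade 3 or higher events so far in the ongoing VRC07-523LS study, and section 9.4.1 reports nothing above Grade 1 in a prior multi-dose VOR study.

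A reader might infer that the safety analysis is affected. It is not. Section 9.3 includes everyone who received a dose, and the event counts in the primary endpoint whichever dosing rule is followed.

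**What to change.** By letter of amendment:

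- Make the Grade 3 paragraph of 8.3.5 follow the mandatory stop in 7.2 for related events, name both products, and keep discretion for unrelated events. If discretion is what is intended, amend 7.2 instead and hold both products until the SMC responds.
- State the self-limited reactogenicity exemption, and whether it covers VOR, in the same terms in 7.2 and in the local and systemic reaction paragraphs of 8.3.5. Say whether the local-reaction stop applies at Grade 3.
- State the dosing consequence of a non-haematologic DLT.

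The cost is protocol wording only. Sample size, power and significance level are untouched.

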7 STUDY INTERVENTION DISCONTINUATION AND PARTICIPANT DISCONTINUATION/WITHDRAWAL

7.1 DISCONTINUATION OF STUDY INTERVENTION

Participants for whom study interventions are discontinued should be counseled on the importance of continuing with the study and strongly encouraged to participate in follow-up visits and protocol-specified procedures.

The study will replace all participants who withdraw for reasons unrelated to drug toxicity. If participant withdrawal occurs prior to the initiation of the VRC07-523LS infusions (Step 2), the participant will have inadequate data, and therefore “new” replacement participants can be enrolled. These participants will not be required to return for additional study visits.

Participants who are withdrawn for safety or drug toxicity reasons will continue on study but off study treatment for safety assessments per the end of treatment study visit (see SOE in Section 1.3). Analyses will be completed on all participant samples, including blood, collected at the end of treatment study visit. The data may or may not be included in the final analyses but all clinical safety data will be included in the final Clinical Study Report (CSR).

Participants who are no longer on treatment but are still followed on the study (with safety evaluations obtained per the SOE in Section 1.3) can be terminated from the study for the following reasons:

- Uncontrolled intercurrent illness that prevents continuing study follow-up or regular study visits.
- Noncompliance with protocol-required evaluations.
- Participant request for discontinuation from the study, i.e., withdrawal of consent.
- The Sponsor, Investigator, or regulatory agency terminates the study.

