- Poor adherence to ART as judged by the site Principal Investigator or designee.
- Request by the participant to withdraw from the study and study procedures.
- Request of the participant's primary care provider if she/he thinks the study is no longer in the best interest of the participant.
- Participant judged by the study Principal Investigator to be at significant risk of failing to comply with the provisions of the protocol, as to cause harm to self or seriously interfere with the validity of the study results.
- At the discretion of the IRB/Ethics Committee, FDA, NIH, and other government agencies as part of their duties, Principal Investigator, or industry supporter.

Premature Treatment Discontinuation Evaluations

Participants who begin but do not complete all doses of VRC07-523LS and VOR will be replaced. The collection of virologic, immunologic, and 2nd leukapheresis samples following premature discontinuation will be determined on a case-by-case basis in discussion with the protocol team.

Participants who complete Steps 2 and 3 but are unable to complete the leukapheresis (#2) in Step 4 will contribute to safety analyses and complete an end of study visit. The ability to complete virologic and immunologic endpoint analysis will be determined on a case-by-case basis in discussion with the protocol team. Replacement will be determined by the protocol team based on the ability to complete endpoint analysis.

Delaying VRC07-523LS administration

Under certain circumstances, a participant's scheduled VRC07-523LS infusion may be delayed. The factors to be considered in such a decision include but are not limited to the following:

Within 7 days prior to any study product administration

- Receipt of systemic glucocorticoids (e.g., prednisone or other glucocorticoids) or other immunomodulators (other than nonsteroidal anti-inflammatory drugs [NSAIDs]) – *Please reference paragraph below as these medications are prohibited on study.*
- Pre-infusion abnormal vital signs or clinical symptoms that may mask assessment of study product reaction.
- Inability to dose with VOR due to clinical symptom or laboratory value.
- Intercurrent illness that is not expected to resolve prior to the VRC07-523LS infusion which is assessed by the site principal investigator (or designee) to require delay or withdrawal from the study product administration schedule.

Infusions should not be administered outside the visit window periods.

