Participants who take *systemic glucocorticoids or other immunomodulators* will be followed for safety by completing all the study visits and evaluations associated with the Step they are in when the study team learns of the need for a prohibited medication. If this occurs prior to completing all doses of VRC07-523LS and VOR, DO NOT give any more VRC07-523LS infusions or VOR. Collection of research labs for the time points thereafter will be considered on a case-by-case basis. These participants will be replaced.

Discontinuation of Antiretroviral Therapy

Participants who discontinue ART for any reason will be followed for safety by completing all the study visits and evaluations associated with the Step they are in when the study team learns of the interruption of ART. If the participant discontinues ART prior to completing all doses of VRC07-523LS and VOR, DO NOT give any more VRC07-523LS infusions or VOR. Collection of research labs for the time points thereafter will be considered on a case-by-case basis in discussion with the protocol team. This participant will be replaced.

If the participant discontinues ART before administration of the first dose of VOR and 1st VRC07-523LS infusion, the first VOR dose should not be given and the participant terminates from the study at this time.

If the participant discontinues ART after the first infusion (Day 0) and multiple doses of VOR but before the 2nd VRC07-523LS infusion (Day 60) or prior to completing the second series of multiple VOR doses, study treatment should be discontinued and the participant should continue on study for safety follow-up as noted in the SOE or per the study PI (or designee). Collection of virologic, immunologic, and the 2nd leukapheresis samples following premature discontinuation will be determined on a case-by-case basis in discussion with the protocol team. This participant will be replaced.

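### Section 7.2 lets scheduled safety follow-up of some dosed participants end with their current Step, inside the primary safety window (minor, cheap to fix)

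*Combined protocol and SAP*

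**What the plan says.** Section 7.2 contains several instructions that can apply to the same dosed participant.

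- **Glucocorticoid or immunomodulator users.** Safety follow-up consists of the "study visits and evaluations associated with the Step they are in when the study team learns of the need for a prohibited medication". No more product is given, research samples are decided case by case, and the participant is replaced.
- **ART stoppers, first paragraph.** The same rule, again limited to the current Step: "Participants who discontinue ART for any reason will be followed for safety by completing all the study visits and evaluations associated with the Step".
- **ART stoppers, last paragraph.** For a stop after infusion 1 and multiple vorinostat (VOR) doses, "study treatment should be discontinued and the participant should continue on study for safety follow-up as noted in the SOE" or as the investigator decides.
- **Anyone who discontinues treatment.** They should keep the protocol's visits. "The only exception to this requirement is when a participant withdraws consent for all study procedures or loses the ability to consent freely".
- **Early study discontinuation.** A participant may be withdrawn for, among other reasons, "Development of an illness that requires treatment with medications prohibited in this study".
- **Completers of Steps 2 and 3.** Those who "are unable to complete the leukapheresis (#2) in Step 4 will contribute to safety analyses and complete an end of study visit".

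Section 7.1 adds that people taken off treatment should be "strongly encouraged to participate in follow-up visits and protocol-specified procedures". Its list of reasons for terminating people who are off treatment does not include use of a prohibited drug.

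The primary endpoint is a related Grade 3 or higher AE, laboratory toxicities included. Its window runs from first treatment to the end of study (Section 1.1), through Step 4 (Section 3), or to about 20 weeks after Day 0 (Section 9.4.2). Section 9.3 puts everyone with at least one dose in the safety analysis.

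**The concern.** A dosed participant who starts a systemic steroid in Step 2 is in the primary safety analysis for the whole window. On a literal reading, though, that person's scheduled visits and blood draws may stop when Step 2 stops. Laboratory toxicities are found mainly through scheduled draws, so a later event could go unseen in someone counted as event-free. No section says how a dosed participant with shortened follow-up is handled in the analysis.

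Two study decisions turn on very few events. Section 9.4.2 sets the safety criterion at no more than 1 of 12 participants with a Grade 3 or 4 toxicity. Section 10.1.6 pauses the trial at the second participant with a related Grade 3 or higher AE (self-limited Grade 3 reactogenicity aside) and does not exclude replaced participants. One unseen event could therefore matter, although the chance of it is low.

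**Working it through.** **1. The plan's own figure.** For 0 events in 12, the exact one-sided 95% upper limit is 1 − 0.05^(1/12) = 0.2209. This matches the 0.22 in Section 9.2.

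**2. Planned end-of-study (EOS) visit.** The Section 1.3 footnotes put Visit 12 at 5-8 weeks after Day 60 and EOS 2-4 weeks after Visit 12.
- Nominal: 60 + 35 + 14 = Day 109 to 60 + 56 + 28 = Day 144.
- With infusion 2's window of −3/+14 days, and Visit 12 timed from that infusion as in Section 1.1: 57 + 35 + 14 = Day 106 to 74 + 56 + 28 = Day 158.

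**3. Last scheduled visit if follow-up ends with the Step.**
- Step 2: Day 29. If the Pre-Visit counts as Step 2, it is Day 53-60 (within 7 days of Day 60). The Section 1.3 table places the Pre-Visit under Step 2; Section 8.2 places it under Step 3.
- Step 3: Day 89, which is 109 − 89 = 20 to 144 − 89 = 55 days before nominal EOS.
- Step 4: nothing is lost, because Step 4 contains EOS.

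**4. The fairest yardstick for a Step 2 case.** This person never receives infusion 2, so the relevant mark is Section 8.1's 7 weeks after the last infusion: Day 0 + 49 = Day 49.
- Ending at Day 29: 49 − 29 = 20 days short, covering 29/49 = 59%. The 7-day recording tail for non-serious AEs in Section 8.3.4 extends this to Day 36, still 49 − 36 = 13 days short.
- Ending at the Pre-Visit: 53 − 49 = 4 to 60 − 49 = 11 days past the mark, so it is met.

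Section 2.2 gives a 28-day trough of 272 mcg/mL after one 40 mg/kg dose (n=3), so antibody exposure is still substantial at Day 29.

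**5. Width of the ART limb.** VOR starts on Day 2 and is taken every 72 hours, so dose 2 falls on Day 5. A stop before any treatment leads to termination. A stop after infusion 1 and multiple VOR doses goes to schedule-of-events follow-up. That leaves mainly about Day 0-5 under the Step-limited rule alone.

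**6. Effect on the all-dosed bound (illustration).** Assume 12 fully followed participants plus one truncated participant, no observed events, and risk spread evenly over the nominal window. The documents give none of these assumptions.
- Bound as it would be reported: 1 − 0.05^(1/13) = 0.2058.
- Bound allowing for truncation: solve (1 − p)^12 × (1 − f·p) = 0.05, where f is the fraction of the window observed.

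| Follow-up ends | f | Bound |
|---|---|---|
| Day 29 | 29/144 = 0.201 to 29/109 = 0.266 | 0.2180 to 0.2171 |
| Day 53-60 | 53/144 = 0.368 to 60/109 = 0.550 | 0.2155 to 0.2128 |
| Day 89 | 89/144 = 0.618 to 89/109 = 0.817 | 0.2118 to 0.2087 |

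The shift is 0.2087 − 0.2058 = 0.3 to 0.2180 − 0.2058 = 1.2 percentage points. Even risk probably overstates it, since Section 2.3.1 says most infusion-related events occur in the first 24 hours. The bound stays below the stated 22% throughout.

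**The case against.** The strongest defence is that no real conflict exists. Section 7.2 asks people who stop treatment to keep follow-up as the protocol requires, and the steroid paragraph is where the protocol sets that requirement for this group; the specific rule governs the general one. That reading is possible. It does not explain why the sole-exception sentence omits this group, and it leaves the mismatch with the endpoint window untouched.

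Second, Section 8.1 follows people whose treatment stops for a dose-limiting toxicity or other clinical event until resolution, and has them complete an EOS visit. An illness needing systemic steroids may well qualify. This covers part of the gap. But Section 8.1 also allows the EOS visit once off-study criteria are met, so it fixes no minimum date.

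Third, parts of the amendment letters are not in the text reviewed. The visible parts edit the prohibited-medication list and the early-discontinuation list but not these two paragraphs. An unseen change could remove the point.

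Some stronger readings are tempting but not supported:
- *The plan requires visits to stop at Day 29.* The paragraph does not say follow-up is limited to those visits, and it can be read as a minimum.
- *About three quarters of the safety window is lost.* Measuring Day 29 against Day 109-144 counts time and visits built around an infusion 2 that this person does not receive.
- *ART stoppers generally lose follow-up.* The last ART paragraph sends most of them to the schedule of events, and its reference to not completing the second VOR series might be read to cover even Day 0-5.
- *Withdrawal is a required outcome for prohibited-drug use.* That list says only that a participant may be withdrawn.
- *The 22% bound is wrong.* It refers to 12 fully followed participants, and the affected ones are replaced.

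**Conclusion.** The point holds as a minor inconsistency. The Step-limited wording allows scheduled safety visits to end before the primary endpoint window closes for a small group of dosed participants: mainly steroid or immunomodulator users in Steps 2 and 3, plus a narrow band of ART stoppers. Other text softens this, but none of it guarantees follow-up even to 7 weeks after the last infusion.

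The consequence is limited. Unresolved AEs are followed to resolution or stability (Section 8.1), and related SAEs remain reportable (Sections 8.3.5 and 8.3.6). What remains exposed is a new, non-serious, related Grade 3 or higher AE, most plausibly a laboratory one. The 0/12 bound is unchanged. The all-dosed bound would move by about 0.3 to 1.2 points for one such participant, under an even-risk assumption that probably overstates the shift. The conclusion rests on the literal reading of the two paragraphs and on their not having been changed in amendment text that is not shown.

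**What to change.** In the glucocorticoid/immunomodulator paragraph and the first ART paragraph of Section 7.2, delete the words that tie the visits to the current Step. Then state once that any participant who has received a dose of either product and has not withdrawn consent:

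- continues the schedule-of-events safety assessments (AE review, vital signs, safety laboratory tests), without infusion-, VOR- or leukapheresis-specific procedures; and
- has an EOS visit that does not depend on Visit 12 and falls at least 7 weeks after the last infusion, preferably on the planned calendar of about 20 weeks from Day 0, to match Section 9.4.2.

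The 7-week floor uses the plan's own mark; the 20-week preference goes beyond it, for consistency with the endpoint. Stopping rules, replacement rules and case-by-case research sampling stay as they are.

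The cost is two deletions, one or two sentences, and a few safety visits already in the schedule for a few people who are off treatment.
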